## 12. Significance of work

Replacement of SSBs is an essential recommendation in all dietary guidance on limiting added sugars. However, the role of NSBs to replace SSBs is complicated by its purported adverse effect on the composition of the gut microbiome with associated development of adverse glucose tolerance. Our study will be the first to investigate this question in humans in a randomized controlled trial comparing SSBs, NSBs and water. It will clarify if NSBs are similar to water and will inform the recommendations for dietary guidelines on replacements of added sugars such as SSBs. The proposed project will aid in knowledge translation related to the health effects of NSBs as alternative to sugars, informing evidence-based guidelines and improving health outcomes by educating healthcare providers and patients, stimulating industry innovation, and guiding future research design.

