## 9. HYPOTHESIS

[figure not shown]
1. Replacing SSBs with NSBs or water will change the diversity of gut microbiome after four weeks in regular SSB drinkers.
2. Replacing SSBs with NSBs or water will increase glucose tolerance after four weeks in regular SSB drinkers.
3. Replacing SSBs with NSBs or water will decrease body weight, reduce blood pressure, improve glucose and insulin regulation, decrease blood lipids, decrease ectopic fat, decrease liver fat, decrease body adiposity, and improve diet quality after four weeks in regular SSB drinkers.

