#### **10.04 Sample Size (Power) Calculation.**

The study will be performed in a total of 81 participants. It is powered to show a difference between the water, NSB, and SSB arms in 60 participants in the two primary outcomes. Assuming a drop-out rate of 20 percent, we

would need 75 participants in order to have the power to detect a difference. Since our final recruitment strategy resulted in a large number of participants who made it through the run-in phase, we decided to increase our recruitment in order to replace drop outs and thus will recruit 81 participants.

One primary outcome is in beta diversity of the gut microbiome communities of the participants between water and NSB groups via 16S ribosomal rRNA gene sequencing. We used the micropower R package to compute sample size based upon the power of 16S tag sequencing that can be analyzed using pairwise weighted UniFrac distances [28]. UniFrac is a distance metric based upon the unique fraction of branch length in a phylogenetic tree built from two sets of taxa. Comparison of microbiome samples is performed via weighted UniFrac, which considers the relative abundance of taxa. We simulated the within-group distance as 0.2, and the standard deviation (SD) of within-group distances as 0.07. To detect a weighted UniFrac distance of 0.04, which is smaller than the effect observed in a study of Suez et al. [29] (0.05 derived from figure 5), and considering it is a cross-over study with a within-person correlation of 0.7, and taking into account multiple arms we calculated that for above 95 percent power we would need 60 participants in this study. Assuming a loss of 20 percent, we will recruit 75 participants. We are confident about detecting an alteration in gut microbiome diversity if it exists as previous studies show that small changes in diet causes significant alteration in gut microbiome taxa over a much shorter period (5 to 7 days) in fewer individuals (10 to 25 people) [25, 30].

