Another primary outcome is glucose tolerance, as measured by incremental Area Under the Curve (iAUC) from a 2-hour 75g OGTT. With 60 participants we will have 89 percent power (assuming absolute numbers for mean and SD from our recent unpublished randomized trial) to detect a 20% change in mean iAUC between the water and NSB group if the direction of change is similar to Suez et al. [29] while assuming a within-person correlation of 0.7 and taking into account the three comparisons. The 20% difference for glucose iAUC is based on the minimally important difference proposed by Health Canada to support postprandial blood glucose response reduction claims [31].

This power calculation takes into account adjustment for multiple testing for both primary outcomes using the Benjamini-Hochberg procedure, which is a suggested method by the Food and Drug Administration in its “Multiple Endpoints in Clinical Trials Guidance for Industry” [32]. Benjamini-Hochberg procedure is a step-down method that controls for false discovery rate, while maintaining high power [33, 34]. We will implement a truncated Benjamini-Hochberg method with parallel gatekeeping in which some portion of the unused alpha from each step is reserved for passing to the secondary outcome family if any of the primary outcome is significant. The alpha levels calculated for the primary outcomes is given in table 2. The study is also powered to show a difference between the three arms for secondary outcomes with an  $\alpha=0.0125$ , the lowest possible starting  $\alpha$  for secondary outcomes based upon the truncated Benjamini-Hochberg procedure.

Sub-study: 1H-MRS will be performed in 25 subjects to assess intrahepatic and intramuscular fat. We will have 99% to show a difference in liver fat of 5% between the water and NSB arm for both hepatic and muscle fat assuming a between group SD of 4%, with a correlation of 0.65 and alpha of 0.05.

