**Table 2. Power calculation for primary outcomes between water and NSB arms**

Outcome type	Outcome	Mean change	SD	Correlation	N	Alpha*	Power (Beta)	N (corrected for 20% loss to follow up)
Primary outcomes family								

Primary	Microbiome UniFrac Distance	0.04	0.07	0.7	60	0.0375	98%	75
Primary	Glucose iAUC	44.81 mmol/L/min (20%)	113 mmol/L/min	0.7	60	0.025	89%	75

P-value order will be from largest to smallest.

**10.05 Recruitment.** Participants will be recruited through postings and flyer handouts at St. Michael's Hospital, the University of Toronto, local clinics, and surrounding areas, advertisements in newspapers and on transit, and online listings on Craigslist and Kijiji. Some participants will complete a Survey Monkey to assess general eligibility. We will be utilizing a digital marketing group, TrialFacts, to launch a campaign to recruit participants. TrialFacts works exclusively with research groups to provide specialized patient recruitment services for clinical trials. Participants will be screened first by telephone. Eligible participants will be called in for an information session on the study including being provided the consent form. Those that wish to participate will provide written consent and will subsequently have an in-person screening including blood work. Based on our most recent FACE trial (NCT02459834), we estimate a recruitment rate of 1-2 participants/week and therefore plan to recruit all the participants within a 6-month period. **[name]** will organize the recruitment. Our **MSc candidate #1 ([name], RD)** and our **Research Coordinator** will conduct the screening.

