**Table 2: Latin square randomization for three group cross-over study.**

	Intervention Phase 1	Intervention Phase 2	Intervention Phase 3
Sequence Group 1	A	B	C
Sequence Group 2	B	C	A
Sequence Group 3	C	A	B
Sequence Group 4	B	A	C
Sequence Group 5	A	C	B
Sequence Group 6	C	B	A

*Rows represent all possible sequences and columns represent different intervention phase.*

**10.09 Intervention.** There will be three interventions: Participants will be provided with the SSB of their choice from **Table 3** (355 ml, 140kcal, 42g sugars per can), equivalent NSB (355 ml, 0kcal, 0g sugars per can), or water (355 ml, 0kcal, 0g sugars per can or bottle of still or carbonated water) to replace the amount of SSBs they usually consume ( $\geq 1$ serving/day) as determined in the run-in phase. All intervention beverages will be provided to each participant. They will be instructed to replace their usual SSBs with the study beverages while freely consuming their usual background diets. The calories of the intervention groups will not be matched to allow for “real-world” substitutions using products available on the market. They will pick up one week of their beverage assignment at the first visit of each phase and then will have the remaining three weeks of beverages delivered using an online grocery delivery service (i.e. Grocery Gateway ([www.grocerygateway.com](http://www.grocerygateway.com))). Our **MSc candidate #1 ([name], RD)** and our research coordinator will coordinate the beverage disbursements. The participants will receive relevant drinks during the intervention phase based on their group assignment. They will revert to their usual SSB intake during wash-out phase during which they will not receive any beverages from the study.

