### **11. Statistical Analysis**

Data will be analyzed according to an intention to treat (ITT) principle using mixed models in STATA 14 (StataCorp, Texas, USA). Sensitivity analysis will be performed on the basis of complete data availability for primary endpoints. A separate sensitivity analysis will be performed on the basis of antibiotic use during the trial.

**Primary outcomes.** Repeated measures mixed effect models will be used to assess changes in the two primary outcomes i) beta diversity and ii) glucose iAUC between the groups. Pairwise comparisons between interventions will be performed using Tukey-Kramer adjustment or other appropriate statistics. For all primary outcomes effect modification by sex will be explored. We will use the truncated Benjamini-Hochberg false discovery rate controlling method with parallel gatekeeping procedure to correct for multiple comparisons for all primary outcomes [32].

**Secondary outcomes.** Repeated measures mixed effect models be used to assess changes in weight, waist circumference, fasting glucose, 2hr plasma glucose, and MATSUDA. Pairwise comparisons between interventions will be performed using Tukey-Kramer adjustment or other appropriate statistics. For all secondary outcomes

effect modification by sex will be explored. We will use the truncated Benjamini-Hochberg false discovery rate controlling method with parallel gatekeeping procedure to correct for multiple comparisons for all secondary outcome comparisons [33] if at least one primary outcome reaches significance. If none of the primary outcomes reach significance, the secondary outcomes will be analyzed as exploratory variables with no adjustment for false discovery rate.

**Exploratory and adherence outcomes.** Repeated measures mixed effect models will be used to assess changes in all exploratory outcomes without controlling for false discovery rate. Pairwise comparisons between interventions will be performed using Tukey-Kramer adjustment or other appropriate statistics. Effect modification by sex will be explored.

**Subgroup Analysis.** A priori analysis will be conducted by age, sex, ethnicity, baseline BMI, baseline WC, baseline FPG, baseline 2hPG (OGTT), baseline iAUC, medication use, sweetener blend (intervention), beverage type (intervention), and background sweetener use.

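### Does the plan need a similarity margin or confidence-interval rule because Section 12 says the trial will clarify whether NSBs are similar to water?

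*Combined protocol and SAP*

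**What the plan says.** Section 12 (Significance of work) describes what the trial will contribute: "It will clarify if NSBs are similar to water and will inform the recommendations for dietary guidelines on replacements of added sugars".

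Section 10.04 and its power table size both primary outcomes on this contrast; the table is headed "Power calculation for primary outcomes between water and NSB arms". The aim there is detection. The trial as a whole is described so: "It is powered to show a difference between the water, NSB, and SSB arms in 60 participants in the two primary outcomes". For glucose iAUC the calculation is "to detect a 20% change in mean iAUC between the water and NSB group", with 89% power at 60 participants. The 20% is described as the "minimally important difference proposed by Health Canada to support postprandial blood glucose response reduction claims".

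The hypotheses listed in Section 9 are about replacing SSBs, for example "Replacing SSBs with NSBs or water will increase glucose tolerance after four weeks in regular SSB drinkers". The objectives in Section 8 have the same form. None states that NSBs and water are equivalent.

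Section 11 specifies repeated-measures mixed models, and then: "Pairwise comparisons between interventions will be performed using Tukey-Kramer adjustment or other appropriate statistics". A truncated Benjamini-Hochberg procedure covers multiplicity. The only rule for non-significant primary outcomes concerns the status of the secondary outcomes. No similarity margin and no confidence-interval rule appears.

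**The concern.** A difference test and a similarity question do not match. A significant NSB-water difference answers the question in Section 12. A non-significant one may mean that the two are close, or only that the estimate is imprecise. With no margin stated in advance, a reader could fear that any p-value above the threshold will be reported as similarity, and that guideline writers will rely on it. A margin chosen after the results are known would be open to challenge. The matter is not marginal to the trial, since NSB against water is the contrast on which both primary outcomes were sized.

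**Working it through.** **Inputs.** From the power table in Section 10.04, glucose iAUC row: difference 44.81 mmol/L/min (20%), SD 113, correlation 0.7, N = 60, alpha 0.025. Section 10.04 adds that the three comparisons are taken into account. Sidedness is not stated; two-sided is assumed.

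**Step 1: reproduce the plan's figure.**
- SD of the paired difference = 113 × √(2 × (1 − 0.7)) = 87.53.
- SE = 87.53 / √60 = 11.30.
- Two-sided alpha 0.025/3 with 59 df gives a critical t of 2.730.
- Non-central t power for 44.81 = 88.7%, against the stated 89%. It reproduces.

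**Step 2: precision.**
- Implied mean = 44.81 / 0.20 = 224.05.
- 95% half-width = 2.001 × 11.30 = 22.61, or 10.1% of the mean.

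**Step 3: which non-significant results leave 20% open?**
- The 95% interval excludes 44.81 when the observed difference is below 44.81 − 22.61 = 22.20 (9.9%).
- The largest non-significant difference at 0.025/3 is 2.730 × 11.30 = 30.85 (13.8%). Its upper 95% limit is 30.85 + 22.61 = 53.46 (23.9%).
- So an observed difference below 22.20 is non-significant and excludes 20%. One from 22.20 to 30.85 is non-significant and inconclusive.

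**Step 4: how often does the inconclusive band occur?** With the observed difference D normal around the true value and SE 11.30, the probability that |D| lies between 22.20 and 30.85 is:

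| True difference | Inconclusive band |
|---|---|
| 0 | 4% |
| 5% | 13% |
| 10% | 28% |
| 20% | 9% |

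At a true difference of zero, the 95% interval lies wholly inside ±44.81 in 94.8% of trials. At a true 20% difference the test is non-significant in 11.3% of trials, but the interval lies inside ±44.81 in only 2.5%.

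**Step 5: dependence on the error levels.** The band above tests at 0.025/3 and reads the interval at 95%.
- Both at 0.05: the largest non-significant difference is 22.61, so the band is 22.20 to 22.61.
- Both at 0.025/3: the half-width is 30.85, so the band starts at 44.81 − 30.85 = 13.96 and runs to 30.85.

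**Step 6: would a formal rule have one obvious form?** Power to place the interval inside the margin, true difference zero, N = 60:

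| Margin | 95% CI | 90% CI |
|---|---|---|
| ±20% | 94.8% | 97.7% |
| ±15% | 67% | 80% |
| ±10% | 5% | 25% |

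The tightest margin with 80% power is about 16.6% with a 95% interval and about 15% with a 90% interval. Feasibility therefore turns on two choices, margin and interval level, that the documents do not settle. The 20% comes from guidance on reduction claims, and nothing in the plan justifies it as a similarity margin. For beta diversity, 0.04 is given only as an effect to detect.

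**The case for a change.** The best case for a change is that it is cheap. A sentence in Section 11 would say that the NSB-water difference is reported with its interval and that non-significance alone is not similarity; otherwise one clause of Section 12 could be reworded. Section 12 ties the question to dietary guidelines, Section 10.02 keeps the statistician blinded so a rule could be fixed in time, and a ±20% margin would have ample power at the planned size.

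Some of this stands. Non-significance is not evidence of similarity, the plan has no rule, and the inconclusive band is real under every choice of error levels in the working. But the argument shows that a rule could be added, not that the plan goes wrong without one. The sentence about non-significance restates normal practice. A formal rule would need a margin and interval level on which statisticians would reasonably differ, and beta diversity would need its own. Nor are non-significant results uninformative as a class: on these inputs any observed difference below 22.2 excludes the plan's 20%.

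**Conclusion.** The concern does not call for a change. The gap is an unstated reading rule attached to one clause of significance text, and analysts fill it sensibly by reporting the NSB-water difference from the primary model with its confidence interval. The background in Section 7 raises a possible harm from non-nutritive sweeteners; a difference test suits that question, and its iAUC power is correctly calculated.

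If NSB and water truly have the same iAUC, about 95% of trials would exclude a 20% difference with an ordinary 95% interval, and about 4% would fall in the inconclusive band. The band is widest in consequence at a true difference near 10%, where about 28% of trials would be inconclusive; the reported interval would show that.

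These figures assume 60 completers, SD 113, correlation 0.7 and two-sided testing. A lower correlation would widen the interval: at 0.5, power for ±20% with a 95% interval falls to about 73% (normal approximation). The conclusion does not rest on the exact values. It rests on the planned tests being valid and on no section saying that a non-significant result will be called similarity.

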## 13. TIMELINE

Milestone	Date
Grant awarded	Apr 2017
Ethics Approval	Jan 2018
MTA/DTA Approval	Feb 2018
Recruitment commenced	Feb 2018
First patient randomized	Mar 2018
Recruitment completed	Aug 2018
Last patient completed	Mar 2019
Laboratory analysis completed	Oct 2019
Data analyses completed	July 2020
Manuscript completed	Nov 2020
Manuscript submitted	Dec 2020
Manuscript accepted	Jan 2021

## 14. BUDGET

BUDGET ITEM	SUBTOTAL
PERSONNEL	\$150,000.00
MICROBIOME	\$30,000.00
PARTICIPANTS	\$42,000.00
LABORATORY	\$70,000.00

BEVERAGES	\$3,000.00
OFFICE SUPPLIES	\$2,500.00
RECRUITMENT	\$20,000.00
KNOWLEDGE TRANSLATION	\$12,500.00
GRAND TOTAL	\$330,000.00

**15. Genetic Testing: This aspect of the study will be optional and is not part of the main objectives of the study**

**Objective:** To determine whether there are any genetic differences between individuals in their response to study beverages.

**Background.** There is considerable interest in the scientific community to study how genes may influence response to diet. In terms of taste our diets tend to be bland containing lower salt and also less sugar. The genes controlling these tastes may therefore determine intake [52, 53]. This is an example of why comprehensive genetic analysis, due to the implication of a growing number of genes of interest, would be helpful. We will, however limit our analyses to specific genes currently known to affect dietary response. Generally, the effect of genes on diet is very modest and usually requires significant numbers of people to detect the difference. It therefore has very limited clinical relevance. We may therefore pool data from across our future studies (typically 30-80 participants per study). A bio-bank will be established for the proper storage and management of these samples.

We hope to make our initial findings known to participants at the end of the study, especially if we discover specific groups for which certain types of dietary advice may prove advantageous. Genetic testing results are solely for use in this study and will not be shared with any third parties (i.e. insurance companies or the hospital).

**Analyses.** The DNA will be extracted from “buffy coat” of white blood cells obtained after plasma has been removed from citrated blood samples drawn at week 0 of phase I or any time point during the main study. Therefore, no additional blood samples will be required for this study.

The genes of interest will include those related to the effectiveness of dietary change on blood glucose, cholesterol and associated measurements including blood pressure, taste preference, and other related genes which may influence response to diet.

**Incidental findings.** *An incidental finding is a finding concerning an individual research participant that has potential health or reproductive importance and is discovered in the course of conducting research but is beyond the aims of the study[54].* Any incidental findings (as defined above) obtained from screening or during the course of the main study from laboratory tests, ultrasound or MRI images will be provided to the family physician for further investigation. The participant will be notified in reassuring terms and advised to follow-up with their family physician. In this sub-study, if genes identified have clinical implications the advice of experts in that particular field will be sought to arrange appropriate counseling for the participant. The family physician’s involvement would be sought if the participant consents to it. However, the chances of incidental findings are limited since only specific genes known to affect dietary response will be studied.

**Banking of Samples.** Blood samples (de-identified) will be stored at the University of Toronto (at the Medical Science Building or the Fitzgerald Building) until all planned analyses have been undertaken-usually about 3 to 5 years. Optional longer-term banking will be made available to all participants for storage periods of 30 years after study completion to allow for use in future secondary and exploratory analyses in relation to the objectives

of the current research project. At the end of each storage period, samples will be destroyed by autoclaving. We are currently investigating the process of setting up a Biobank to efficiently and securely store and manage these samples; the necessary application will be sent to the St. Michael's REB once the project proposal is drawn up. Presently the use and ultimate destruction of these samples will be the responsibility of the investigator, [name]. However, detailed information on the organization and management will be in the biobank proposal that will be submitted to the REB in the near future.

